Determination:	subjects per treatment group) was selected to have 80 % power to determine non-inferiority, based on the assumption of 20 % vaccine efficacy (VE), a 2 % or greater influenza attack rate in the active comparator (ARV _C) for protocol-defined ILI due to RT-PCR-confirmed influenza caused by any viral type/subtype and a 10 % dropout rate. Non-inferiority will be concluded if the lower bound of the two-sided 95 % confidence interval (CI) is greater than -20 %.
	Please note that the sample size of 12,120 subjects will also provide sufficient power (over 80 %) for the secondary-endpoint (protocol-defined respiratory illness caused by any influenza viral type/subtype).
	In the event of an insufficient attack rate of confirmed influenza (minimum of 198 cases), the study will be either continued or extended into another season to enrol more subjects and a protocol amendment will be issued to address changes to the enrolment plan.
Study Population:	Non-institutionalized male and female subjects 65 years of age and older, with no acute or evolving medical problems and with no clinically significant disease at the time of vaccination, will be included in this study.
Dosage and Administration:	On Day 0, subjects will receive one intramuscular (IM) injection into the deltoid region of the arm of 0.5 mL of 30 µg/strain of the Quadrivalent VLP Influenza Vaccine or 0.5 mL of the 15 µg/strain of the Quadrivalent comparator vaccine (eg: Fluarix Tetra/Quadrivalent/® and/or FluLaval® Tetra/Quadrivalent).
Study Design:	This is a randomized, observer-blind, active comparator-controlled, multicenter, Phase 3 efficacy study.
	The influenza strain composition of the vaccines used in this study will be based on the recommended World Health Organization (WHO) strains for vaccination in the 2018-2019 season in the northern hemisphere.
	Subjects will participate in this study for approximately eight to ten months, during which a first visit will be scheduled on Day 0 for screening and vaccine administration. A phone contact will be made on Days 1 and 8, specifically for review of the subject's safety and concomitant medication data. A visit to the investigator site will occur on Day 21 for immunogenicity assessments (CMI, HI, MN, and SRH) for a subset of 420 subjects from pre-defined sites in North America (210 subjects

Medicago R&D Inc. Page 13 of 90

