3.6. Determination of Sample Size

The sample size of approximately 12,120 subjects (6060 subjects per treatment group) was selected to have 80 % power to determine non-inferiority, based on the assumption of 20 % VE, a 2 % or greater attack rate in the active comparator (ARV $_{\rm C}$) for protocol-defined ILI caused by any influenza viral types/subtypes, and a 10 % dropout rate. Non-inferiority will be concluded if the lower bound of the two-sided 95 % CI is greater than -20 %.

In the event of an insufficient attack rate of confirmed influenza (minimum of 198 cases), the study will be either continued or extended into another season to enrol more subjects and a protocol amendment will be issued to address changes to the enrolment plan.

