6. GENERAL ASPECTS FOR STATISTICAL ANALYSIS

6.1. General Methods

All statistical procedures will be completed using (SAS®) version 9.4 or higher.

Unless otherwise stated, all statistical testing will be two-sided and will be performed using a significance (alpha) level of 0.05. Two-sided 95% confidence intervals (CI) will be provided when relevant.

Continuous variables will be summarized using descriptive statistics, including number of subjects (n), mean, median, standard deviation (SD), minimum (Min) and maximum (Max).

For categorical variables, summaries will include counts of subjects and percentages. Percentages will be rounded to one decimal place.

All summaries will be presented by treatment group and age group, unless otherwise specified.

All subject data, including those derived, will be presented in individual subject data listings. All listings will be sorted by subject number, date/time and visit. The vaccine group (VLP and Comparator) as well as subject's age stratum will be stated on each listing.

A subject who is randomized but does not receive study drug will be included in the subject data listings. All pre- and post-vaccination results, including repeated and unscheduled assessments, will be included in the data listings. Data collected at unscheduled visits that occurred outside the time windows specified in the protocol will be included in the data listings but will not be included in the analyses.

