8.2. Analysis of Primary Efficacy Endpoint

The primary efficacy endpoint defined in Section 4.1.1 will be analyzed using the PP set as outlined below:

For the primary endpoint, VE will be evaluated as the relative risk of subjects vaccinated with Quadrivalent VLP Influenza Vaccine (30 μ g/strain) or an active comparator to develop protocoldefined ILI as a result of laboratory-confirmed infection with any influenza virus (RT-PCR) \geq 14 days after vaccination.

VE will be calculated using the following formula:

$$VE=(1-RR)=(1-ARV_V/ARV_C)*100 \%$$

Where:

RR = relative risk

 ARV_V = attack rate in subjects vaccinated with the Quadrivalent VLP Influenza Vaccine; and

ARV_C = attack rate in subjects vaccinated with an active comparator.

Non-inferiority will be concluded if the lower limit of the two-sided 95 % CI for relative VE is > -20 % for the primary endpoint. If non-inferiority is demonstrated, VE of the VLP vaccine will be tested for superiority over the active comparator as an exploratory analysis (VE for superiority testing will use the same definitions as in the primary endpoint). Superiority will be concluded if the lower limit of the two-sided 95 % CI for relative VE is > 9 % for the primary endpoint.

The primary endpoint will be summarized descriptively with VE and its 95% CI.

The analyses of the primary efficacy endpoint will be repeated for the FAS.

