8.3. Analysis of Secondary Efficacy Endpoints

The secondary efficacy endpoints which are defined in Section 4.1.2 will be analyzed in the following manner:

VE and 95% CI will be calculated for the secondary efficacy endpoints using the same formula indicated for the primary efficacy analysis.

For secondary efficacy endpoints, the sub-analyses (VE and its 95% CI) by each strain (homologous A/Michigan/45/2015 [H1N1], homologous A/Singapore/INFIMH-16-0019/2016 [H3N2], homologous B/Colorado/06/2017 and homologous B/Phuket/3073/2013), where applicable, and by age group (65-74 and >75) will be summarized.

Non-inferiority will be tested using the same criterion as with the primary endpoint; superiority testing will be conducted if non-inferiority is concluded (the same criterion as with the primary endpoint will be used for superiority testing).

All the secondary efficacy analyses will be based on the PP and will be repeated for the FAS as well.

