8.3.1. Multiplicity

Multiplicity adjustment will not be done for the secondary efficacy endpoints. The inclusion of secondary endpoints is intended to yield supportive evidence related to the primary efficacy endpoint by providing additional clinical characterization of the treatment effect. Therefore, the use of statistical strategy to control the overall Type 1 error is not necessary.

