8.4. Analysis of Exploratory Endpoints

The exploratory efficacy endpoints 1 and 2 which are defined in Section 4.1.3 will be analyzed using the same formula indicated for the primary efficacy analysis. The sub-analyses (VE and its 95% CI) by age group will be summarized.

Non-inferiority will be tested using the same criterion as with the primary endpoint; superiority testing will be conducted if non-inferiority is concluded (the same criterion as with the primary endpoint will be used for superiority testing).

Summaries of study outcomes for those with 'respiratory illness' or systemic illness (ILI) will be presented for the overall population as well as by age and treatment group.

In addition, an individual listing will be included to present details of the results of RT-PCR and typing (laboratory-confirmed influenza vaccine matched, mismatched strains, or un-typed strains), respiratory illness symptoms, and ILI by subject and age stratum.

For the exploratory efficacy endpoint 3 defined in Section 4.1.3, the presence of VE waning can be tested by the linear trend (i.e., the proportional hazards) in the scaled Schoenfeld residuals from the Cox proportional hazard model [Petrie 2016, Durham 1998]. Specifically, it will be analyzed as below:

Step 1: Fit a regular Cox proportional hazard model with the treatment group as the main effect, and Fluarix will be coded as the reference group in the model.

Step 2: Find the scaled Schoenfeld residual from the Cox proportional hazard model in step 1. The scaled Schoenfeld residual has value at all event-time for the main effect (treatment group);

Sample SAS® Code:

```
Proc phreg data = ADZ (with the appropriate analysis dataset);
model AVAL*Censor(1) = TRTP / (ref = `Fluarix');
output out=res wtressch = TRTP_r;
run;
Note: Censor indicates censoring status: 1 = Censored; 0 = protocol-defined ILI due to laboratory-confirmed influenza.
```

Step 3: Fit a linear regression on the scaled Schoenfeld residuals against event time.

Sample SAS® Code:

```
Proc GLM data = res;
model TRTP_r = AVAL;
  ods output ParameterEstimates= prms;
run;
Note: AVAL in step 2 and 3 is the event time for the primary efficacy endpoint, protocol-defined ILI caused by any influenza viral type/subtype.
```

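### Formal non-inferiority and superiority conclusions on the secondary VE endpoints and exploratory endpoints 1 and 2 are not made conditional on the primary endpoint meeting non-inferiority

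*SAP*

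**What the plan says.** **Level and criteria.** SAP 6.1 sets the general level: "all statistical testing will be two-sided and will be performed using a significance (alpha) level of 0.05". SAP 8.2 concludes non-inferiority on the primary if the "lower limit of the two-sided 95 % CI for relative VE is > -20 % for the primary endpoint". It then tests superiority, labelled exploratory, and concludes it if the "lower limit of the two-sided 95 % CI for relative VE is > 9 % for the primary endpoint".

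**Secondary endpoints.** SAP 8.3 gives these endpoints the same two-step rule: "Non-inferiority will be tested using the same criterion as with the primary endpoint; superiority testing will be conducted if non-inferiority is concluded". SAP 8.3.1 makes no multiplicity adjustment. Its reason is that the secondaries are there to support and further characterise the primary result: "Therefore, the use of statistical strategy to control the overall Type 1 error is not necessary".

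**Exploratory endpoints 1 and 2.** SAP 8.4 uses the same sentence, beginning "Non-inferiority will be tested using the same criterion as with the primary endpoint", and contains no multiplicity statement. Exploratory endpoint 3 (waning) has no non-inferiority test.

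**Protocol.** The synopsis (Statistical Methods) and sections 12.3.2 and 12.3.3 carry the same rule. The synopsis paragraph on sample size adds that 12,120 subjects "will also provide sufficient power (over 80 %) for the secondary-endpoint" of respiratory illness caused by any influenza type. Protocol 12.2 and SAP 3.6 do not repeat that remark.

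The only condition stated anywhere runs from non-inferiority to superiority within the same endpoint. No test order is given.

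**The concern.** The reason given in SAP 8.3.1 and the rule given in 8.3 do not fit together. Endpoints that only support the primary need VE and a confidence interval. Here each one also gets a formal non-inferiority conclusion at the full level, and possibly a superiority conclusion. If the primary misses the -20% limit, the plan as written still allows a statement of non-inferiority on an overlapping version of the same outcome: the matched-strain subset of the same ILI cases, or a broader case definition that contains them. The primary result would then have failed while its supportive evidence was reported as a success, with no wording in the plan to prevent or qualify that.

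**Working it through.** **Inputs from the documents.** 6060 per arm, 10% dropout, 2% comparator attack rate and assumed VE 20% (SAP 3.6); margin -20%, so RR 1.2 (SAP 8.2); score limits for RR (SAP 8.2.2); two-sided 0.05 (SAP 6.1).

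**The plan's own figure.** SAP 3.6 says the sample size "was selected to have 80 % power to determine non-inferiority, based on the assumption of 20 % VE". With p_C = 0.02, p_V = 0.016, R = 1.2 and one-sided 0.025:

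- Variance: 0.016 × 0.984 + 1.44 × 0.02 × 0.98 = 0.043968.
- Distance from the margin: 0.016 - 1.2 × 0.02 = -0.008.
- n per arm: 0.043968 × (1.960 + 0.842)² / 0.008² = 5393 evaluable. Divided by 0.9 this is 5993, or 11,986 in total, against 12,120 stated (1.1% lower).
- With 6060 × 0.9 = 5454 evaluable per arm, score-test power is 81.4%. Expected cases are 5454 × 0.036 = 196, against the stated minimum of 198.

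The design is reproduced, so 5454 per arm is used below.

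**Test used in the simulation.** z = (R·p_V0 - p_V) / √{[q_V(1-q_V) + R²·q_C(1-q_C)]/n}, where p_V0 is the observed comparator rate and the q's are the rates fitted under q_V = R·q_C. Non-inferiority is concluded if z > 1.96. Counts were drawn as Poisson in disjoint cells (ILI or respiratory illness only, matched or other strain), and the nested endpoints were built by adding cells, with 200,000 trials per setting.

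**Assumptions not in the documents.** Confirmed respiratory illness is 10% to 60% more frequent than confirmed ILI, and the matched share is 30% to 70%. The true RR is 1.2 for every laboratory-confirmed endpoint.

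**Why nesting does not remove the problem.** For nested counts the correlation of two test statistics is roughly the square root of the event ratio. At 30% more respiratory illness, primary and any-strain respiratory illness correlate at about √(1/1.3) = 0.88. At a 50% matched share, primary and matched ILI correlate at about √0.5 = 0.71. These are high, but leave room for one endpoint to pass when the other fails.

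| Extra respiratory illness / matched share | Primary alone | Primary or secondaries 1-3, at least one false conclusion | Primary fails, at least one of secondaries 1-3 passes |
|---|---|---|---|
| 10% / 70% | 2.6% | 5.0% | 2.4% |
| 30% / 50% | 2.7% | 6.2% | 3.6% |
| 60% / 30% | 2.7% | 7.3% | 4.6% |

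The first and last rows are the corners of the assumed range. The middle of the range is about 6% and about 3% to 4%.

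**With the condition on the primary.** The last column becomes zero, and the third column falls back to the primary's own 2.6% to 2.7%.

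**Cost at the design VE** (RR 0.80 throughout, 30% more respiratory illness): non-inferiority on any-strain respiratory illness is concluded in about 90% of trials without the condition and about 80% with it.

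**Where the condition does not help.** Let the primary truly have VE 20% while matched strains have RR 1.2. The other strains then have RR (0.8 - 1.2m)/(1 - m), which is 0.63 at matched share m = 0.3 and 0.40 at m = 0.5. A false matched-strain conclusion (secondaries 1 or 2) occurs in 3.6% to 3.7% of trials with or without the condition, because the primary nearly always succeeds when these pass.

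The any-cause endpoints (secondary 4, exploratory 2) are outside these figures. Non-influenza illness pulls their true RR towards 1, so a pass there need not be a false rejection of that endpoint's own null.

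**The case against.** The strongest reply is that the SAP decided this openly. There is one primary endpoint, its error rate is intact, and the documents nowhere claim that 2.5% holds across the secondary and exploratory set. Superiority is exploratory even for the primary. Forgoing full multiplicity control among supportive endpoints is a defensible choice. All of that stands, and it limits the point to what may be concluded after a failed primary.

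Several stronger readings are tempting but unsupported:

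- *That the plan says these conclusions are drawn whether or not the primary succeeds.* It does not say so; it is silent, and the missing condition is read from that silence.
- *That every exploratory endpoint is affected.* Endpoint 3 has no non-inferiority test.
- *That the error reaches about 10%.* That figure (9.9% to 10.7%) adds the mismatched endpoint and counts the two vaccination-history groups of secondary endpoint 5 as two tests. SAP 12 says only that occurrence and VE with CI will be summarised for those groups. Leaving them out but keeping the mismatched endpoint gives 7.7%, and 5.1% after a failed primary (30% more respiratory illness, half matched).
- *That strain and age sub-analyses carry conclusions as well.* SAP 8.3 describes them as VE with its CI.
- *That the synopsis power remark makes a secondary endpoint confirmatory.* It appears only in the synopsis and assigns no such role.

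What the reply does not answer is the mismatch itself. A supportive role explains reporting estimates without error control. It does not explain drawing formal conclusions when there is no primary success to support, and 8.4 offers no reason at all.

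**Conclusion.** The point holds in a limited form. Formal non-inferiority and superiority conclusions on the secondary VE endpoints and exploratory endpoints 1 and 2 lack a condition that the primary met non-inferiority, and this does not fit the supportive role on which SAP 8.3.1 relies. With a true RR of 1.2 on all laboratory-confirmed endpoints, false non-inferiority somewhere among the primary and secondaries 1 to 3 occurs in about 6% of trials rather than 2.6% to 2.7%, and about 3% to 4% of trials would claim it after the primary failed. The sizes depend on the assumed event mix; the gap in the text does not.

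A reader might infer that conditioning on the primary gives control across all endpoints. It does not. It restores about 2.6% only when the primary's null is also true, and it leaves error among the secondaries as it was once the primary succeeds. This is an inexpensive improvement to the plan and no threat to the primary analysis.

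**What to change.** Add to SAP 8.3 and 8.4: *Non-inferiority and superiority conclusions on secondary endpoints and exploratory endpoints 1 and 2 are drawn only if the primary endpoint met non-inferiority in its primary (PP) analysis; otherwise VE and 95% CI are reported without a conclusion.*

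Record the change in SAP 12, because the Protocol synopsis, 12.3.2 and 12.3.3 carry the unconditional rule. Make it before unblinding and database lock, by which point Protocol 12.3 requires the SAP to be final.

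A fixed test order among the laboratory-confirmed secondaries, each at two-sided 0.05 and stopping at the first failure, is optional. It is needed only if the sponsor wants error control among them after a successful primary.

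The cost is wording: every estimate and interval is still reported. The named downside is the loss of a secondary conclusion when the primary fails, which is the fall from about 90% to 80% for any-strain respiratory illness at the design VE.

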8.3.1. Multiplicity

Multiplicity adjustment will not be done for the secondary efficacy endpoints. The inclusion of secondary endpoints is intended to yield supportive evidence related to the primary efficacy endpoint by providing additional clinical characterization of the treatment effect. Therefore, the use of statistical strategy to control the overall Type 1 error is not necessary.

8.3.2. Methodology for computing CI

8.3.2.1. Wilson Score 95% CIs

The 95% CIs will be calculated in the same way as for the primary analysis mentioned above (Section 8.2.2).

8.4. Analysis of Exploratory Endpoints

The exploratory efficacy endpoints 1 and 2 which are defined in Section 4.1.3 will be analyzed using the same formula indicated for the primary efficacy analysis. The sub-analyses (VE and its 95% CI) by age group will be summarized.

Non-inferiority will be tested using the same criterion as with the primary endpoint; superiority testing will be conducted if non-inferiority is concluded (the same criterion as with the primary endpoint will be used for superiority testing).

Summaries of study outcomes for those with 'respiratory illness' or systemic illness (ILI) will be presented for the overall population as well as by age and treatment group.

In addition, an individual listing will be included to present details of the results of RT-PCR and typing (laboratory-confirmed influenza vaccine matched, mismatched strains, or un-typed strains), respiratory illness symptoms, and ILI by subject and age stratum.

For the exploratory efficacy endpoint 3 defined in Section 4.1.3, the presence of VE waning can be tested by the linear trend (i.e., the proportional hazards) in the scaled Schoenfeld residuals from the Cox proportional hazard model [Petrie 2016, Durham 1998]. Specifically, it will be analyzed as below:

Step 1: Fit a regular Cox proportional hazard model with the treatment group as the main effect, and Fluarix will be coded as the reference group in the model.

Step 2: Find the scaled Schoenfeld residual from the Cox proportional hazard model in step 1. The scaled Schoenfeld residual has value at all event-time for the main effect (treatment group);

Sample SAS® Code:

```
Proc phreg data = ADZ (with the appropriate analysis dataset);
model AVAL*Censor(1) = TRTP / (ref = `Fluarix');
output out=res wtressch = TRTP_r;
run;
Note: Censor indicates censoring status: 1 = Censored; 0 = protocol-defined ILI due to laboratory-confirmed influenza.
```

Step 3: Fit a linear regression on the scaled Schoenfeld residuals against event time.

Sample SAS® Code:

```
Proc GLM data = res;
model TRTP_r = AVAL;
  ods output ParameterEstimates= prms;
run;
Note: AVAL in step 2 and 3 is the event time for the primary efficacy endpoint, protocol-defined ILI caused by any influenza viral type/subtype.
```

Step 4: The slope and p-value will be output. $VE(t)=1-\exp(beta(t))$, VE(t) waning (smaller with time) is corresponding to the increasing beta(t). Thus, a positive slope with significant p-value (<0.05) will indicate VE is waning though time.

All the exploratory efficacy analyses will be based on the PP and will be repeated for the FAS as well.

9. ANALYSIS OF IMMUNOGENICITY

9.1. Immunogenicity Evaluation

Immunogenicity will be evaluated by the humoral immune response (HI, MN, and SRH assays) and the CMI response induced in subjects on Days 0 and 21 in a subset of 420 subjects (210 from each treatment group) from selected sites. The North American sites selected for this subset of 420 subjects will be pre-defined prior to study start and will target providing a representative age distribution. The number of subjects in each age group (65 to 74 years of age and 75 years of age and older) included in the immunogenicity analyses will be similar in proportion to that of the overall study.

9.2. Analysis of Secondary Endpoints

The secondary immunogenicity endpoints are defined in Section 4.3.1.

HI antibody titers will be analyzed and evaluated as follows:

- GMTs of HI antibody: The point estimates and the corresponding two sided 95 % CI by treatment group and strain will be calculated as the antilog of the mean and 95 % CI of log transformed titer values on Days 0 and 21;
- SC rate: The point estimates and the corresponding two-sided 95 % CI for subjects achieving SC by treatment group and strain will be calculated and reported;
- SP rate: The point estimates and the corresponding two-sided 95 % CI for subjects achieving SP by treatment group and strain will be calculated and reported.
- GMFR: the geometric mean of the ratio of GMTs (Day 21/Day 0).

MN antibody response against the homologous influenza strains on Days 0 and 21 will be analyzed as follows:

- GMTs of MN antibody on Days 0 and 21(as defined above for HI);
- SC rate: the proportion of subjects in a given treatment group with either a ≥ 4-fold increase in reciprocal MN titers between Day 0 and Day 21 or a rise of undetectable MN titer (i.e. 7.1) pre-vaccination (Day 0) to an MN titer of ≥ 28.3 at Day 21 post-vaccination.
- GMFR: the geometric mean of the ratio of GMTs (Day 21/Day 0).

SRH antibody response against the homologous influenza strains will be analyzed as follows:

- GMAs of SRH antibody on Days 0 and 21;
- SC rate: proportion of subjects in a given treatment group showing at least 50% increase in GMA between Days 0 and 21;
- SP rate: the proportion of subjects in a given treatment group attaining an area ≥ 25 mm² following vaccination (Day 21);
- GMFR: the geometric mean of the ratio of GMAs (Day 21/Day 0).

The GMFR will be derived by using ANCOVA to model the difference in the log of the titer values between Day 21 and Day 0, with treatment group as main effect and baseline titer as covariate

The GMTs, GMFRs, SP and SC rates of the HI antibody assay, the GMTs, GMFRs and SC rates of and the MN antibody assay, and the GMAs, GMFRs, SC rates, and SP rates for the SRH antibody assay will be compared between the treatment groups using descriptive statistics and 95% CI.

For SC rate and SP rate, Fisher's exact tests will be used. GMT for HI, MN and GMA for SRH will be compared between treatment groups using the ANOVA model. GMFR for HI, MN and SRH will be compared using the ANCOVA model.

A sub-analyses stratified by age group for the secondary immunogenicity endpoints will performed.

The analyses of the secondary immunogenicity endpoints will be repeated for the FAS.

An individual listing will be provided to include all assay results (HI, MN and SRH) and whether a particular subject has seroconverted/seroprotected based on IPP set.

In addition, the below listed figures will be generated:

- Reverse Cumulative Distribution Curves (RCDC) for Homologous Strains Measured and Heterologous Strains Measured by HI based on IPP.
- RCDC for Homologous Strains Measured by HI based on FAS.
- RCDC for Homologous Strains Measured by MN based on IPP.
- RCDC for Homologous Strains Measured by SRH based on IPP.

